ALT or AST > 10 ULN	Interrupt DFP. When levels return to < 5 ULN, restart DFP at 50% of the last dose and after 1 month scale it back up to the former dose.	Interrupt DFX. When levels return to < 5 ULN, restart DFX at 50% of the last dose and then escalate by 10 mg/kg/day at 1 month intervals provided that value increase does not recur.

CONFIDENTIAL

Severe skin rash	No dose adjustment.	Interrupt DFX . Once resolved, restart DFX at 50% of the last dose and then escalate by 5 mg/kg/day at two-weeks intervals.
Ferritin \leq 500 ng/ml	Reduce DFP to 50% of last dose. If ferritin is still <500 ng/ml at subsequent monthly evaluation, DFP may continue having consulted the Coordinating Investigator. When value returns > 500 ng/ml DFP can be scaled up to full dose.	Reduce DFX to 50% of last dose. If ferritin is still <500 ng/ml at subsequent monthly evaluation, DFX may continue having consulted the Coordinating Investigator. When value returns > 500 ng/ml restart DFX at 50% of the last dose and then escalate by 10 mg/kg/day at 1 month intervals.
Neutropenia(neutrophil count $<1500/\text{mm}^3$ and $\geq 1000/\text{mm}^3$ in two consecutive measurements)*	Interrupt DFP and monitor neutrophil count every 1-3 days or more frequently. When value returns $> 1500/\text{mm}^3$ for two consecutive measurements, and if deemed safe by the investigator, restart DFP at the last dose after having consulted the Coordinating Investigator.	Interrupt DFX and monitor neutrophil count every 1-3 days or more frequently. When value returns $> 1500/\text{mm}^3$ for two consecutive measurements, and if deemed safe by the investigator, restart DFX at the last dose after having consulted the Coordinating Investigator.
Moderate Neutropenia (neutrophil count $<1000/\text{mm}^3$ and $> 500/\text{mm}^3$) OR Severe Neutropenia/Agranulocytosis (neutrophil count $< 500/\text{mm}^3$) Infection	Interrupt DFP. Exit from the protocol.	Interrupt DFX. Exit from the protocol.

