Arthralgia	Interrupt DFP until neutrophil count is checked. If neutrophil count is $> 1500/\text{mm}^3$, two consecutive measurements, and if deemed safe by the investigator, restart DFP at the last dose after having consulted the Coordinating Investigator. If symptoms persist after appropriate treatment, reduce DFP to 50% of last dose until resolution and then scale it back up to the former dose.	Interrupt DFX until neutrophil count is checked. If neutrophil count is $> 1500/\text{mm}^3$, two consecutive measurements, and if deemed safe by the investigator, restart DFX at the last dose after having consulted the Coordinating Investigator. If symptoms persist after appropriate treatment, reduce DFX by 50% until resolution and then escalate by 10 mg/kg/day at 1 month intervals to the former dose.
Nausea/ Abdominal Pain/	If symptoms persist after appropriate treatment, reduce DFX	If symptoms persist after appropriate treatment, reduce DFX

Vomiting	DFP to 50 mg/kg/day until resolution and then scale it back up to the former dose.

* For details on clinical management of all neutropenia, please refer to Section 7.3.18 "Neutrophil count and Neutropenia management" and Section 16.6 "Instructions for rapid notification of Neutropenia".
	

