Separate information sheets describing the study's objectives and procedures, elaborated in a form which will take into account the cultural and linguistic differences in the study population, will be provided to the parent/legal guardian prior to the submission of the Informed Consent Form. The parent/legal guardian will be provided an Informed Consent Form in his/her National language to be signed only upon agreement of the terms and conditions included in the document.

All the time necessary to freely decide the involvement of a subject in the clinical trial will be made available.

In addition, and in accordance with the "Ethical Considerations for Clinical Trials Performed in Children", Recommendations of the *ad hoc* group for the development of implementing guidelines for Directive 2001/20/EC relating to GCP in the conduct of clinical trials on medicinal products for human use, separate information sheets specifically elaborated for children and adolescents, in language and wording appropriate to age, psychological and intellectual maturity, and taking into account the cultural and linguistic differences, will be provided to each patients in order to inform him/her on the study's objectives and procedures and obtain his/her assent to the participation to the study.

According to the European Ethical Recommendations (2008), if the child's assent is not obtained, this should be documented in the Informed Consent Form which is signed by the parent/legal representative and investigator.

The Informed Consent Form must be signed and personally dated by the legal representative and the Investigator / Co-Investigator. The original copy of the signed forms will be retained with the source documents in the trial site and a copy will be given to the family/participant.

Upon parents' and/or participant's consent, a letter will be sent to the participant's primary care doctor informing him/her of the involvement of his/her young patient in the trial, the treatment, the concomitant other medicinal products not permitted.

Carers and participants are free to refuse to participate to the trial or withdraw their consent at any time and for every reason.

After the patient has entered the trial, the clinician must remain free to give alternative treatment to that specified in the protocol, at any stage, if he/she feels it to be in the best interest of the patient.

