7.3.18 Neutrophil count and Neutropenia management

The measurement of absolute neutrophil counts will be done weekly (\pm 7 days), possibly at each scheduled visit for an early identification of cases of neutropenia and agranulocytosis. In case of infection neutrophil count should be monitored more frequently. Neutrophil count for checking exclusion criteria must be assessed between day -9 and day -7 of the screening period.

Neutropenia is defined as any ANC < 1500/mm³ confirmed in two consecutive measurements. If both consecutive counts are below $1.5 \times 10^9/L$ but are not within the same range, a third count is required to determine the severity category. Neutropenia is considered to be resolved when ANC is $\geq 1.5 \times 10^9/L$ on 2 consecutive counts.

Mild Neutropenia* (ANC $\geq 1000/mm^3$ and < $1500/mm^3$ in two consecutive measurements)

Moderate Neutropenia* (ANC $\geq 500/mm^3$ and < $1000/mm^3$ in two consecutive measurements)

Severe Neutropenia/Agranulocytosis* (ANC < $500/mm^3$)

The handling and follow up of the patient will depend on the severity of the neutropenia (mild, moderate, severe/agranulocytosis) as follows.

Mild Neutropenia:

- treatment must be interrupted and patient's ANC must be monitored every 1-3 days, or more frequently, until resolution of the event, defined as two consecutive ANC $\geq 1500/\text{mm}^3$.
- If the patient has a mild neutropenia and develops signs of infection (fever), therapy must be interrupted immediately and ANC must be obtained and monitored every 1-2 days, or more frequently, until resolution of the event.
- Provide protective isolation; treat the patient as per clinical need and per local protocol (antibiotic therapy, admission to hospital if clinically indicated). If possible, hemoculture, throat swab, viral studies (CMV, parvovirus, hepatitis A/B/C), serum ALT, BUN, creatinine will be collected.
- Therapy with DFP or DFX and continuation of trial can be restarted once all symptoms have been resolved and when it is deemed safe by the Investigator, after having consulted the Coordinating Investigator, in accordance with Table 4, Section 6.3 "Dose Adjustment".

Moderate Neutropenia

- treatment must be interrupted and the patient must be withdrawn from the study and monitored until resolution of the event;

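### Minor inconsistency: for a first neutrophil count between 500 and 1000/mm³, Table 4 orders exit without a confirming count, while Section 7.3.18 requires two counts and gives no action for the first

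*Combined protocol and SAP*

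**What the plan says.** **Section 6.3, Table 4.** The mild row (below 1500, at least 1000/mm³) applies when the count is low "in two consecutive measurements". The next row covers moderate neutropenia, "Moderate Neutropenia (neutrophil count $<1000" and above 500/mm³, together with severe neutropenia below 500/mm³. It carries no repeat-count condition. Its action is "Interrupt DFP. Exit from the protocol", with the same order for DFX. A footnote adds: "For details on clinical management of all neutropenia, please refer to Section 7.3.18".

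**Section 7.3.18.** The general definition is "Neutropenia is defined as any ANC < 1500/mm³ confirmed in two consecutive measurements". If two low counts fall in different severity ranges, a third decides the category. The moderate line, with an inclusive lower bound, reads "500/mm^3$ and < $1000/mm^3$ in two consecutive measurements". The severe line reads "Severe Neutropenia/Agranulocytosis* (ANC < $500/mm^3", with no two-count condition. Confirmed moderate neutropenia leads to interruption and withdrawal.

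**Section 16.6** uses the two-count definition for expedited reporting.

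**Section 9, item 5** lists moderate or severe neutropenia among the reasons to discontinue, without saying which definition applies. Sections 9 and 11.13 count prematurely withdrawn patients as treatment failures. Section 11.2 limits PP1, the primary population, to patients whose composite endpoint is available at baseline and after one year.

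**The concern.** The two sections can dispose of the same child differently, and the difference cannot be undone, because exit is permanent. Since the mild row states the repeat-count condition, a site could reasonably take its absence one row lower as deliberate. That site would withdraw a child whose second count is normal or only mildly low. The child becomes a treatment failure and probably leaves PP1, because no one-year composite will exist.

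A site that relies on Section 7.3.18 alone meets a different gap: nothing tells it what to do while a count of, say, 800/mm³ awaits confirmation. Routine counts are weekly, ±7 days. After a count taken on its scheduled day, the next routine count could therefore fall as late as 7 + 7 = 14 days later, with no instruction in that section to hold the drug. What remains is the general provision in Section 7.3.2 that "the clinician must remain free to give alternative treatment to that specified in the protocol".

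**Working it through.** The plan gives no figure on this point to reproduce. The check is a comparison of the texts, followed by a rough sizing.

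**1. Same counts, two sections**

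| Successive counts (/mm³) | Table 4, read literally | Section 7.3.18 |
|---|---|---|
| 800, 900 | exit at the first count | moderate confirmed; withdraw |
| 800, 1600 | exit at the first count | second count not below 1500: no neutropenia |
| 950, 1200 | exit at the first count | ranges differ: third count decides; restart possible if mild |
| 450 | exit | severe line has no two-count condition: withdraw |

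The clear conflict is confined to a first count between 500 and 1000/mm³ that the second count does not confirm as moderate.

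**2. What adding only the two-count phrase would do.** Table 4 is the only place that tells the site to stop the drug at a first count in this range. Adding the phrase without an interim hold would remove that instruction.

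**3. Size in the analysis.** Inputs are the planned success rates of 67.5% (DFP) and 65% (DFX), 194 per arm randomised and 155 per arm evaluable (Section 11.12: 388 and 310 in total), and the margin of -12.5 points. The interval is the unpooled one of Section 11.6:

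L = (p1 - p2) - 1.96 × √[p1(1 - p1)/n1 + p2(1 - p2)/n2]

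The numbers of affected children below are assumptions, because the documents give no rate.

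ITT, 194 per arm, no dropouts:
- Base: 0.025 - 1.96 × √(0.219375/194 + 0.2275/194) = 0.025 - 0.0941, so L = -6.91 points.
- Five successes lost in each arm (64.92% vs 62.42%): L = -7.07.
- Five lost on DFP only (64.92% vs 65%): L = -9.57.
- Losses on DFP only: 10 give -12.22 and 11 give -12.75, so 11 are needed to pass the margin.

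ITT with 20% dropouts counted as failures (0.8 × 67.5 = 54% vs 0.8 × 65 = 52%):
- Base: L = -7.93.
- Five lost in each arm: -7.95. Five lost on DFP only: -10.52.
- Losses on DFP only: 8 give -12.07, and the ninth passes the margin.

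PP1, 155 per arm:
- Base: 0.025 - 1.96 × √(0.219375/155 + 0.2275/155) = 0.025 - 0.1052, so L = -8.02.
- Five would-be successes removed from each arm (66.42% vs 63.83%, 150 each): -8.20.
- Five would-be successes removed from DFP only (66.42%, n = 150): -9.24.
- Five would-be failures removed from DFP only (69.75%, n = 150): -5.76.

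Losses shared by both arms hardly move the limit. Only a one-sided excess does, and in PP1 its direction depends on whether the children removed would have succeeded.

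**The case against.** The strongest reply is that the documents largely resolve this themselves. Table 4 uses a term that Section 7.3.18 defines by two counts, its footnote sends the reader there for all neutropenia, and Section 16.6 agrees. Table 4 is silent on confirmation; it does not waive it. This stands as far as it goes and is why the point is minor. It does not close the matter. In the public text the asterisk for that footnote sits on the mild row, the exit order carries no condition, and the section it points to gives no action for the first count.

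A second reply is that stopping at one count below 1000/mm³ may be deliberate caution in children. That is possible, but the two sections would then still need to agree. It is a good reason to keep a hold at the first count.

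Third, the evidence has limits. The Table 4 row is imperfectly reproduced in the public text (a stray word sits in the severe cell), and the Study Procedures Manual, which holds detailed procedures, is not available. Neither is known to supply the missing condition.

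A reader might also infer more than the documents support:

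- *That the conflict extends below 500/mm³.* The general two-count definition does not exempt severe neutropenia, so a literal question exists. But neither Table 4 nor the severe line of Section 7.3.18 asks for confirmation, and Section 7.3.18 requires immediate interruption and withdrawal.
- *That the rule biases the comparison against DFP.* Section 8 refers to neutropenia induced by DFP, so equal use in both arms cannot be assumed. But the rule is the same in both arms and no rate is given, so neither an imbalance nor its size can be shown.

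**Conclusion.** The inconsistency is real and minor. For a first count between 500 and 1000/mm³, one section orders exit and the other requires confirmation without saying what to do meanwhile. It concerns an operative safety and withdrawal rule, so it should be corrected even though two counts is the better-supported reading.

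Each would-be success withdrawn this way costs its arm about 0.5 points in ITT. At the planned rates, 9 to 11 such losses on DFP alone, with none on DFX, would be needed to bring the expected ITT lower limit past -12.5. Nothing in the documents shows that numbers like these would arise, so the conclusion of the trial is unlikely to change and the sample size is unaffected. These figures rest on the planned success rates and on assumed numbers of affected children. Loss from PP1 is probable, not stated.

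Two neighbouring mismatches are trivial: exactly 500/mm³ falls in no Table 4 category, and resolution is above 1500 in Table 4 but at least 1500 in Section 7.3.18.

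**What to change.** In the moderate row of Table 4 write:

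> ≥500 and <1000/mm³ in two consecutive measurements (third count if ranges differ)

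In Table 4 and Section 7.3.18 add:

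> At a first count ≥500 and <1000/mm³, interrupt the drug and repeat the ANC within 1-3 days; exit if moderate neutropenia is confirmed or if any count is <500/mm³; otherwise restart under the existing mild-neutropenia rule.

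The hold must be bounded at 500/mm³. A hold triggered by any count below 1000/mm³, with exit only on confirmation, would contradict the exit order for severe neutropenia. Leave the exit for any count below 500/mm³ in Table 4 unchanged, and have the sponsor confirm in Section 7.3.18 that it needs no second count.

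The cost is wording in two places, one early repeat count and a short time off drug. If both repeats are normal and each is taken 1-3 days after the previous count, the interruption lasts 2 to 6 days. Slower recovery takes longer, but the 4-week (28-day) suspension limit in Section 9, item 4, still applies. The interim hold is new wording, so the sponsor and the DSMC should confirm it.

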6.4 Handling of investigational medicinal products

DFP will be supplied to the principal investigators by the Sponsor. A separate document will rule the agreement between the Sponsor and the MAH.

DFX will be supplied by each Centre as current therapy in compliance with the applicable national laws in the commercially available package and the label will be integrated in accordance with GMP requirements for the purposes of this study..

In any case, the Sponsor retains the responsibility of ensuring regular supply of both Investigational Medicinal Products (IMP) as ruled by GCP.

Medication labels of both IMPs will comply with the legal requirements of the countries where the study is implemented and be printed in the local language. They will supply no information about the patient. Only the subject identifier will be entered on the medication label under the investigator responsibility before the corresponding medication is handed out to the patient. The storage conditions and the consumption (in-use) period for study drug will be described on the medication label.

Both the experimental and the control medication used in this trial must be kept in an appropriate, secure area (e.g. locked cabinet) and stored according to the conditions specified on the drug labels. The investigator/competent pharmacist must maintain an accurate record of the storage temperature, of the shipment and dispensing of study drugs in a drug accountability ledger, a copy of which must be given to the Sponsor at the end of the study. An accurate record of the date and amount of study drugs dispensed to each subject must be kept by the investigator and made available for inspection at any time.

All drug supplies are to be used only for this protocol and not for any other purposes. Any partly-used or unused drug during the course of the study will be handled according to an *ad hoc* SOP. Destruction of unused/unusable investigational medicinal products and their empty containers should be carried out only after any discrepancies have been investigated and satisfactorily explained and the reconciliation has been accepted.

At the conclusion of the study, and, as appropriate during the course of the study, the investigator will follow the Sponsor's indications concerning the local disposal of any surplus and/or rejected materials. Unused/unusable investigational medicinal products and of all the empty drug containers should therefore not be destroyed without prior written authorisation by the Sponsor according to the conditions specified on an *ad hoc* SOP.

6.5 Blinding

Blinding is not foreseen for this trial because of the different pharmaceutical forms and posology of IMPs which would have heavily impacted on the study feasibility.

6.6 Randomisation

Patients will be stratified before randomisation into two groups according to age (<10 years and \geq 10 years) considering their different capabilities in undergoing cardiac MRI T2*.

After stratification patients will be randomised on Day 0 of the study at the 1:1 ratio to one of two treatment groups. One group will be treated with DFP, the other (control) group with DFX.

Patients will be assigned a sequential patient number in each center at screening. Each patient will be unambiguously identified by a 6-digit subject identifier consisting of a 2-digit centre number and the 4-digit, sequential patient number. This subject identifier is unique and will not be changed throughout the entire study. Subject identification numbers of patients that did not meet the entrance criteria and were not randomised will not be re-used.

Randomisation will be determined centrally and balanced by country. The randomisation list will be printed out in advance at the start of the study. Since the number of recruited patients *per* centre cannot be determined *a priori*, a larger number of randomised numbers *per* country will be generated to allow a greater than anticipated number to be studied in the event that the enrolment rate in some specific centre is below expectations.

The randomisation number and the assigned treatment will be recorded in the source documents as well as in the CRF of the corresponding patient.

No fixed number of patients per age group will be specified upfront. However at least 10% of the patients recruited into the study will be aged from 1 month to less than 6 years.

7. CLINICAL AND LABORATORY EVALUATIONS

7.1 Study outline

This study includes: a run-in period (maximum 28 days), a 12 months treatment period and a follow-up visit 1 month after last administration, as detailed below in **Figure 1**.

Figure 1: Study outline

The study procedures and outline develop as follows:

- Run-in period (day -28 to -1) divided in:
 - *Screening period* (day -28 to -7): Patients on their standard chelator schedule will be screened for eligibility. Two visits are foreseen in this period, the first one (Visit 1, between day -28 and day -8) to describe the study to the patient and to his/her parents and to obtain the informed consent, the second one (Visit 2, day -7) to assess the inclusion/exclusion criteria (see **Section 5.1** and **Section 5.2**)

- *Washout period* (day -6 to -1): At day -6 patients will discontinue their ongoing chelator to start the washout phase.

The recruitment will start with the first eligible patient having signed informed consent and will continue for 12 months or less if the required number of patients has been reached.

- Treatment and observation period (month 1-month 12): the treatment period will start on Day 0 during V3 with randomization and will continue for 12 months. Patients will be visited every month. At each visit, assessments as detailed in **Table 5** will be conducted with a constant attention to the minimisation of pain and distress to the patient.

Ferritin levels for efficacy assessments will be evaluated quarterly (centrally). Additionally, ferritin levels for patient's medical management will be evaluated monthly (locally).

Cardiac MRI T2* in patients above 10 years of age able to undergo the MRI evaluation without sedation (regardless of their assignment treatment) will be assessed at baseline (V3), at month 6 (V9) and at the end of treatment (month 12, V15).

Liver MRI will be assessed in all patients able to undergo the MRI evaluation without sedation (regardless of their assigned treatment) at baseline (V3) and at the end of treatment (month 12, V15).

Patients will continue with their regular transfusional regimen.

7.2 Visit schedule and assessments

The schedule of all study evaluations is outlined in **Table 5**.

Table 5. Visit schedule and evaluations

CONFIDENTIAL

DEEP Consortium
DEEP2-Efficacy/Safety Study Protocol

Protocol No. DEEP-2

Ocular and audiometric test ⁸				X											X	
Concomitant medications				X	X	X	X	X	X	X	X	X	X	X	X	X
Medical events				X												
Adverse events					X	X	X	X	X	X	X	X	X	X	X	X
Body height/weight	X			X	X	X	X	X	X	X	X	X	X	X	X	X
Pubertal staging				X					X							X
Compliance					X	X	X	X	X	X	X	X	X	X	X	X
CHQ questionnaire				X					X						X	X ¹⁰
Healthcare Resources					X	X	X	X	X	X	X	X	X	X	X	X
	
¹Results of platelet count, neutrophil count, haemoglobin and serum creatinine must refer to blood test performed on day -9 to day -7. Serum creatinine must be assessed in duplicate (for the assessment of inclusion/exclusion criteria only)
 
²Treatment drug should be administered in the clinic under supervision of qualified staff and time recorded accordingly. A sample (2 mL) for the assessment of peak drug concentrations should be collected within 4 hours after dosing according to the sparse sampling scheme specified in the SPM
 
³Liver MRI is allowed to be performed \pm20 days from the scheduled date
 
⁴Cardiac T2*MRI is allowed to be performed \pm20 days from the scheduled date
 
⁵Serum creatinine and serum creatinine clearance(calculated through Schwartz formula) will be performed weekly (\pm 7 days from the scheduled date) for the first month of treatment and monthly thereafter
 
⁶Neutrophil counts must be performed weekly (\pm7 days from the scheduled date) from the start of treatment
 
⁷Serum transaminases, bilirubin and alkaline phosphatase will be checked before the initiation of treatment, every 2 weeks during the first month and monthly thereafter
 
⁸Ocular and audiometric examination are allowed to be performed \pm20 days from the scheduled date
 
⁹Ferritin at V1, V4, V5, V7, V8, V10, V11, V13 and V14 will be evaluated only at the local laboratory. All other ferritin assessments will be evaluated at both the local and central laboratory/ies.
 
¹⁰Central ferritin, haematology/biochemistry and CHQ will be evaluated also in case of withdrawal (withdrawal visit).
															

The clinical assessments will be conducted at each scheduled visit. The timing of each visit is listed in **Table 5**. Each visit will be scheduled at the same day of the month \pm 7 days. MRI evaluations (cardiac and hepatic) will be allowed \pm 20 days deviation from the scheduled visit.

Further information is provided in the following sections and detailed procedures for conducting each assessment are provided in the Study Procedures Manual (SPM).

At each visit, following completion of all procedures, the patient will be discharged from the unit.

